#### **Study Population:**

This is a prospective cohort study that will be performed at the University of Arizona Medical Center (UAMC), a Level I Trauma center. Patients who undergo emergent surgery for trauma induced enteric injuries

involving the stomach, small bowel, or colon (ex: gun-shot wounds, stab wounds, blunt colon perforation) or the non-traumatic emergent general surgical pathologies involving the above hollow viscera.

Retrospective review of our database over the past 3 years identified total of 276 patients: 157 patients underwent emergent surgery for trauma related colon injuries and 43 patients due to acute perforated diverticulitis. In addition, 76 patients underwent emergent abdominal surgery for perforated viscus excluding colonic pathologies. Based on these results, we conservatively estimate an average of 90 patients per year will require emergent abdominal surgery for perforated viscus. Thus, we anticipate **enrolling 20 patients** over the 1 year period. This will be followed by data collection, follow-up period, data analysis and report/manuscript about research findings.

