### **Subject Inclusion Criteria:**

Patients 18 years and older

Emergent surgeries involving enteric injuries e.g. traumatic injuries involving stomach, small bowel, or colon; or the non-trauma emergent general surgical pathologies involving the above hollow viscera.

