#### **Statistical Analysis:**

#### **Sample Size Calculation:**

- A. Event Rate Assumption(s): <5%
- B. Study Group (%): 100%
- C.  Comparator or  Sham Group (%): historic cohort from previous 3 years.
- D. Power Estimation:  95%  90%  85%  80% or Other – Specify: \_\_\_\_%
- E. Evaluable Rate Consideration: Specify: \_\_\_\_%
- F. Sample Size Calculation: 20 Total Number of Subjects. When population is not divided evenly, please specify how it will be divided and rationale for doing so:
- G. Interim Analysis - Sample Size Re-calculation:  Yes  No  Specify rationale:
- H. Number of Centers Projected: 1

This is an observational prospective study with no concurrent arm for comparison; we will use historic data from our center over the last 3 years to analyze results. The advantage of this approach is that there was no change in medical providers among trauma surgeons in the last 3 years. We also have a robust prospectively collected trauma registry that allows performing this analysis. We will identify patients who have undergone emergent abdominal surgery with hollow viscus violations, and had undergone wet-to-dry dressing changes. A Propensity matching analysis will be performed to match patients from the historic cohort to the current patients by demographics, disease severity and laboratory tests. A univariate analysis, independent t-test, and a Kaplan-Meier survival analysis will be performed to compare rate of infection, time-to-closure, and cost analysis.

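### The planned propensity match leaves out trauma versus non-trauma origin, although both are eligible, so the VeraFlo and historical groups can differ in case mix.

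*Combined protocol and SAP*

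**What the plan says.** Under Subject Inclusion Criteria, eligibility covers traumatic bowel injury "or the non-trauma emergent general surgical pathologies involving the above hollow viscera". Clinical Hypotheses and Study Population describe the same two groups.

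The narrative under Sample Size Calculation gives the control rule: "We will identify patients who have undergone emergent abdominal surgery with hollow viscus violations, and had undergone wet-to-dry dressing changes". This does not restrict by origin. The propensity match is then to "match patients from the historic cohort to the current patients by demographics, disease severity and laboratory tests". The same paragraph says "We also have a robust prospectively collected trauma registry that allows performing this analysis", and it names no other data source. Elsewhere, the paragraph on the historical cohort under Subject Exclusion Criteria provides for a review of charts using the prospective cohort's eligibility rules. Recruitment Methods and Consenting Process also says that controls are found through chart review.

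Study Population reports a three-year review that "identified total of 276 patients". It counts "157 patients underwent emergent surgery for trauma related colon injuries and 43 patients due to acute perforated diverticulitis", and a further "76 patients underwent emergent abdominal surgery for perforated viscus excluding colonic pathologies".

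**The concern.** With no concurrent arm, the comparison depends on the historical controls resembling the VeraFlo patients. A propensity score is built to balance what is put into it; other factors are balanced only so far as they correlate with those variables. Injured patients and patients with, for example, perforated diverticulitis can plausibly differ in age, comorbidity, time from contamination to operation and infection risk. If the share of non-trauma cases differs between the groups, part of any difference in SSI, time to closure or cost may be a difference in case mix. Bowel site would not stand in for origin, because the review has colon cases of both kinds.

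The sample makes this harder to ignore. With 20 VeraFlo patients, one infection moves the observed rate by 1/20 = 5 percentage points.

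**Working it through.** **Inputs.** From Study Population: 157 trauma colon cases, 43 perforated diverticulitis, 76 non-colonic perforations of unstated origin, total 276. From Sample Size Calculation: 20 VeraFlo patients.

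**The plan's own figures.** 157 + 43 + 76 = 276, as stated. 276/3 = 92 per year, consistent with the statement that "we conservatively estimate an average of 90 patients per year will require emergent abdominal surgery for perforated viscus".

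**Non-trauma share.** The text does not say how the 76 divide, so the share has two bounds:
- all 76 are trauma: 43/276 = 15.6%
- none of the 76 is trauma: (43 + 76)/276 = 119/276 = 43.1%

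**Expected non-trauma VeraFlo patients**, if enrolment mirrors the review: 20 × 0.156 = 3.1 and 20 × 0.431 = 8.6, so about 3 to 9.

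**How often a match could cross origins (illustration).** Assume that the control pool has the same mix p, that each VeraFlo patient gets one control, and that the match carries no information on origin. The expected number of non-trauma patients given a trauma control is 20 × p × (1 − p):
- p = 0.156: 20 × 0.156 × 0.844 = 2.6
- p = 0.431: 20 × 0.431 × 0.569 = 4.9

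The same number is expected in the other direction. Exact matching on origin brings both to 0. Matching variables that correlate with origin would lower these counts by an amount the documents do not allow one to compute.

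**Whether crossed matches bias the comparison.** If both groups have the same mix, crossed matches cancel on average in a comparison of group rates. Bias arises when the mixes differ, and two things leave room for that:
- Chance. The binomial standard deviation of the non-trauma share among 20 patients is √(p(1 − p)/20): √(0.156 × 0.844/20) = 0.081 and √(0.431 × 0.569/20) = 0.111, or about 8 to 11 percentage points.
- Selection. VeraFlo patients must be consented around an emergency operation. Controls must have had wet-to-dry dressings, and the sections that describe their source do not agree.

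**Size of the bias.** It would be the difference in mix multiplied by the difference in SSI rate between origins. The documents give neither quantity, so no figure can be computed.

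**The case against.** The best reply is that the match headings are broad. Age falls under the first. The second could take in the comorbidity and severity scores listed under Procedures Involved in the Human Research (Charlson and APACHE II) and the Injury Severity Score in the Data Collection Flow Sheet. Source of infection and procedure performed are also to be collected, so an analyst might well use them. This stands in part: such variables may carry some of the difference. But the severity heading is undefined. A comorbidity index or a physiological score does not identify origin, and an injury score gives no common scale for a patient without injury. The plan does not tie source of infection or procedure to the match.

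Two stronger readings are tempting, and the documents do not support them.

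First, a reader might infer from the mention of a trauma registry that the control pool is trauma-only. Two other sections provide for chart review, one of them under the prospective cohort's criteria, and the selection rule under Sample Size Calculation admits any hollow viscus case. The documents do not describe what the registry holds. What remains is an inconsistency about the control source.

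Second, a reader might estimate the bias from rates in the Introduction. The 9.8% and 32.1% both come from one study of trauma patients and differ by closure method, and the 14 to 32% range is not split by origin. The plan also states no comparator rate, only an assumed event rate below 5%, so there is no stated contrast against which to judge a bias.

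**Conclusion.** The concern holds as an omitted matching factor. Both origins are eligible, the non-trauma share of reviewed cases is 15.6% to 43.1%, and the one planned adjustment does not name origin. Followed as written, the match can cross the two populations and does not secure the same mix in both groups.

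The share rests on the review describing the eligible mix. It is approximate, because the counts precede the wet-to-dry restriction and the upper bound needs all 76 non-colonic cases to be non-trauma. The 3 to 9 patients further assume that enrolment follows the review. Whether the omission would change the result, and in which direction, cannot be said from the documents. The case for acting is that the factor is known for every patient and inexpensive to include.

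**What to change.** In the narrative under Sample Size Calculation, add origin (trauma or non-trauma) to the match. Match exactly on it first, then run the propensity match within each stratum. State in advance that, if a stratum has too few controls, origin enters the propensity model as a term instead. Report SSI counts by origin in both groups as description only; with perhaps 3 to 9 non-trauma VeraFlo patients, a test within stratum would tell little.

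Reconcile that narrative with the historical-cohort paragraph under Subject Exclusion Criteria and with Recruitment Methods and Consenting Process, so that one stated control source covers both trauma and non-trauma cases. The same edit can settle the control period, given as 2008–2013 in one place and the previous three years in another.

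This is a change of analysis wording. Origin should be known from the indication for surgery, so no new visit or measurement is needed. The downside is fewer candidate controls per stratum, by an amount that depends on the enrolled mix and on how many historical patients had wet-to-dry dressings.

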### **Primary Outcome:**

The primary outcome of the study will be the rate of superficial and deep incisional surgical site infection, as defined by the Center for Disease Control and Prevention (CDC) definitions. (30).

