#### **Superficial incisional SSI**

Must meet the following criteria:

Infection occurs within 30 days after any NHSN operative procedure (where day 1 = the procedure date), including those coded as 'OTH'\*

and

involves only skin and subcutaneous tissue of the incision

and

patient has at least one of the following:

- a. purulent drainage from the superficial incision.
- b. organisms isolated from an aseptically-obtained culture of fluid or tissue from the superficial incision.
- c. superficial incision that is deliberately opened by a surgeon, attending physician or other designee and is culture positive or not cultured

and

patient has at least one of the following signs or symptoms: pain or tenderness; localized swelling; redness; or heat. A culture negative finding does not meet this criterion.

- d. diagnosis of a superficial incisional SSI by the surgeon or attending physician or other designee .

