#### **A. Secondary Efficacy Endpoint(s):**

1. Time to complete wound closure
2. Cost analysis: Cost-effectiveness ratio is determined by the net cost of material supplies, human labor, and the health effect of an intervention. The net cost includes the direct cost of drug, the equipment and their administration, and also on any savings that might be achieved by using this method, such as reduction in hospital stay, decrease of antibiotic usage.
3. Pain score as defined by the Wong-Baker Pain Scale related to the VeraFlo presence/manipulation.

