### **Procedures Involved in the Human Research:**

We will approach patients upon the diagnosis to consent them for this prospective study. During the process, the details of the trial will be reviewed along with potential risks and benefits, the endpoints of interest and the process by which these endpoints are evaluated. When notified of trial enrollment, the patient or their legal representative will be given the opportunity to withdraw from further data and sample collection. Those who consent will be enrolled to collect data on outcomes, baseline parameters and follow-up period to evaluate efficacy of VeraFlo for management of contaminated abdominal wounds after emergent surgery. VAC with 1/4% Dakin's solution will be placed immediately at the end of the surgery for the first 3 postoperative days, followed by delayed primary closure on postoperative day 4. Wound will be swabbed at the end of surgery before placing the VAC and before skin closure on Day 4. All follow-ups will be performed as a standard of care.

Data collected will include the following: demographics (i.e. BMI), hemodynamic parameters at the time of presentation and operation, source of infection, imaging studies outcomes, lab tests, surgical procedure performed and its duration, vasopressors, estimated blood loss and transfusion records, antibiotics used and duration, comorbidities (Charlson Morbidity Index, APACHE II), trauma registry data, and complications (if any) during their hospital stay and follow-up in clinic, length of stay (in ICU and in hospital), intra-abdominal wound culture, wound closure details, pain level, cost, wound appearance (recorded by photograph), wound culture, infection, time of nursing care.

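### No rule for death before wound closure: Kaplan-Meier with deaths censored would overstate the proportion closed, by an amount the documents do not allow one to fix

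*Combined protocol and SAP*

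**What the plan says.** The comparative analysis is a single sentence under Sample Size Calculation in the Statistical Analysis section. It lists a univariate analysis and a t-test, and ends: "a Kaplan-Meier survival analysis will be performed to compare rate of infection, time-to-closure, and cost analysis". Three methods are listed for three outcomes. None is assigned to an outcome, and no event, time origin or censoring rule is defined.

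The outcomes are set earlier. Under Primary Outcome, "The primary outcome of the study will be the rate of superficial and deep incisional surgical site infection". The first secondary efficacy endpoint is "Time to complete wound closure". In the VeraFlo cohort, the instillation therapy is "followed by delayed primary closure on postoperative day 4" (Procedures Involved in the Human Research). The comparator is a historical wet-to-dry cohort, to be propensity matched on demographics, disease severity and laboratory tests.

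Mortality is an item on the Data Collection Flow Sheet. It appears in no primary, secondary or safety endpoint and in no planned analysis. The only rule for incomplete data, under Withdrawal of Subjects, covers patients who withdraw. No expected death rate is given.

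**The concern.** Death before closure is a competing event: once it happens, closure cannot. Standard Kaplan-Meier practice censors the patient at death, which treats that patient as someone who would later have closed at the same rate as the survivors. The complement of the curve then estimates closure in a population where nobody dies, not the share of patients whose wounds were closed.

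Deaths are plausible here. The inclusion criteria begin "Emergent surgeries involving enteric injuries e.g. traumatic injuries involving stomach, small bowel, or colon", and the data to be recorded include "vasopressors, estimated blood loss and transfusion records, antibiotics used and duration, comorbidities (Charlson Morbidity Index, APACHE II". Those are markers of illness severity, not a death rate, but they show that the investigators expect some very sick patients.

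The two cohorts are also exposed differently. VeraFlo wounds are planned to stay open for four days, whereas wet-to-dry wounds may stay open longer. The bias therefore need not cancel in the comparison. With 20 patients, each one is 5 percentage points of any proportion, so handling of even one death is visible. If the rule is not written in advance, it can be chosen once the results are known.

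**Working it through.** The plan states no figure for closure, mortality or censoring, so there is none to reproduce. The checks below compare one minus Kaplan-Meier (deaths censored) with cumulative incidence (death competing).

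**Inputs from the documents:** 20 VeraFlo patients; closure planned for postoperative day 4; follow-up to the two-week clinic visit.

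**Assumptions, not in the documents:** median closure of 14 days in controls; 30-day mortality m of 10% or 20%; constant hazards unless stated.

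**1. VeraFlo cohort.** Suppose k of 20 die before day 4 and all others close on day 4. The deaths leave the risk set, everyone still at risk closes, and Kaplan-Meier gives 100%. Cumulative incidence is (20 − k)/20:
- k = 1: 19/20 = 95%
- k = 2: 18/20 = 90%

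**2. Controls.** Closure hazard c = ln 2/14 = 0.04951 per day. Death hazard d = −ln(1 − m)/30, which is 0.00351 for m = 10% and 0.00744 for m = 20%.

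One minus Kaplan-Meier at day t is 1 − exp(−ct). Cumulative incidence is c/(c + d) × [1 − exp(−(c + d)t)].

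| Day | 1 − KM | CIF, m = 10% | CIF, m = 20% | Excess of KM |
|---|---|---|---|---|
| 14 | 50.0% | 48.9% | 47.8% | 1.1 to 2.2 points |
| 30 | 77.4% | 74.3% | 71.2% | 3.0 to 6.2 points |

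Day 14 is the relevant row, because prospective follow-up ends at about two weeks.

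**3. Net effect on the comparison (VeraFlo minus control).** Apply the same mortality to both cohorts. With constant hazards, VeraFlo deaths by day 4 are 1 − exp(−4d) = 1.4% or 2.9%, so VeraFlo cumulative incidence is 98.6% or 97.1%.
- Day 14: Kaplan-Meier difference 100 − 50.0 = 50.0 points; cumulative incidence difference 98.6 − 48.9 = 49.7, or 97.1 − 47.8 = 49.3. Kaplan-Meier slightly overstates the advantage.
- Day 30: Kaplan-Meier 100 − 77.4 = 22.6 points; cumulative incidence 98.6 − 74.3 = 24.3, or 97.1 − 71.2 = 25.9. Kaplan-Meier understates the advantage.
- Day 30, all deaths before any closure in both cohorts: the true difference is (1 − m) × 22.6 = 20.4 or 18.1 points (from unrounded values). Kaplan-Meier overstates again.

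The sign depends on when deaths occur and on the day chosen.

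**4. Infection.** Take a 30-day infection risk of 32% (the top of the range in the Introduction) as the Kaplan-Meier value, with hazard h = −ln(0.68)/30, and put h for c in the formula above. Cumulative incidence is then 30.5% at 10% mortality and 28.9% at 20%. Censoring deaths therefore raises the infection estimate. A crude proportion moves the other way: if 10% die before any infection and stay in the denominator as infection-free, 32% becomes 0.90 × 32% = 28.8%.

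**The case against.** The plan does not say that deaths are censored; that is an inference from common practice. Nor does it make Kaplan-Meier the method for infection. The same loose sentence would make it the method for cost, and the primary outcome is worded as a rate. Both objections stand: the defect is a missing rule, not a wrong one that has been written down.

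A reader might infer that Kaplan-Meier lets early deaths lower the infection rate. Step 4 shows the reverse. Only a crude proportion that counts the dead as infection-free is lowered, and modestly. Relative to the rate among survivors, one such death in 20 lowers an infection risk p by p/20: 0.25 points at 5%, 1.6 points at 32%. A full 5 points per infection-free death arises only in a composite of infection or death, which is a different quantity.

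A reader might also infer that the handling of deaths favours VeraFlo. Step 3 does not support that; the direction is undetermined. Matching on disease severity should also reduce any difference in mortality between cohorts.

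The control bias at day 14 is small beside sampling error: the standard error of a 50% proportion with n = 20 is √(0.25/20), about 11 points. A log-rank test also remains a valid comparison of closure hazards among patients still alive and open. Both are fair. They limit the importance of the point, but neither makes the reported proportion closed correct.

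**Conclusion.** The point holds for time to closure. Kaplan-Meier is named, closure is its natural target, death precludes closure, and no rule for death is given. If deaths are censored, the proportion closed is overstated: by 5 points for each VeraFlo death before day 4 when all others close that day, and by about 1 to 2 points at day 14 in controls under the assumed 14-day median and 10% to 20% mortality.

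Neither assumption comes from the documents. The actual bias may be nil if nobody dies before closure, and its net direction between cohorts cannot be stated. The documents do not support a claim that the plan biases the infection comparison through Kaplan-Meier. For infection, what is missing is a statement of how deaths within the infection window enter the denominator. This is an inexpensive improvement to make before analysis, not a fault that invalidates the study.

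**What to change.** Rewrite the analysis sentence under Sample Size Calculation so that each endpoint has its own method.

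- **Time to closure:** replace Kaplan-Meier by the cumulative incidence (Aalen-Johansen) function with death as a competing event, timed from the index operation in both cohorts. Use a comparison that respects the planned matching. The standard Gray's test does not, so it is not required.
- **Infection:** keep it as a proportion and state how patients who die within the infection window are counted. Add infection or death within that window as a sensitivity analysis. A competing-risk analysis of infection is optional.
- **Deaths:** report them by cohort beside the infection, closure, length-of-stay and cost results, since an early death can also shorten stay and lower cost.

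This needs only revised wording and standard software, because mortality is already on the data collection sheet. The downside is that stated closure proportions become slightly less favourable and the analysis takes a little more work.

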#### **Potential Benefits to Subjects and/or Society:**

Current literature shows strong independent benefits of using Dakin's solution and the negative pressure VAC therapy for managing open contaminated wounds. The solution and the device have also been shown not to be harmful. Currently, there is no standard management protocol regarding the combined utilization of Dakin's solution with VAC therapy, a capability delivered by the KCI VeraFlo. This study aims to study the utility and safety of using the VeraFlo with 1/4% Dakin's solution in managing contaminated abdominal wounds. If it is associated with less SSI and earlier achievement of wound closure, then this technique may serve to standardize the management of contaminated abdominal wounds. It has the potential to decrease the time and resource spent on managing open abdominal wounds as compared to the most common technique of wet-to-dry dressing changes. In addition, this technique has the potential to drastically improve patient comfort, convenience and satisfaction.

